4.10 Endpoints

Primary Endpoints/Outcome Measures

- Rate and severity of local and systemic solicited adverse events (AEs) during 7 days after each study vaccination
- Rate and severity of unsolicited AEs during 28 days after each study vaccination
- Rate and severity of medically-attended adverse events (MAAEs) during 28 days after each study vaccination
- Rate of serious adverse events (SAEs) during 28 days after each study vaccination AEs leading to discontinuation of study vaccination
- AEs leading to study discontinuation
- Rate and severity of laboratory abnormalities (hematology, biochemistry, urinalysis) at Day 56 and 28 days after each study vaccination

Secondary Endpoints/Outcome Measures

- Rate and severity of unsolicited AEs throughout the study
- Rate and severity of medically-attended adverse events (MAAEs) throughout the study
- Rate of serious adverse events (SAEs) throughout the study
- Rate and severity of laboratory abnormalities (hematology, biochemistry, urinalysis) throughout the study
- GMT and the geometric mean fold increase in serum antibody titer post-vaccination over Day 1 (baseline) at Days 56 and 224 (Phase 1a) or Days 56 and 168 (Phase 1b):
 - Neutralizing activity against multiple variant spike protein-expressing pseudovirus, and/or PRNT neutralizing activity against wild-type SARS-CoV-2 virus and the variant Beta (B.1.351) in all participants
 - RBD antibody titers against wild-type variant spike protein measured by ELISA

- GMT and the geometric mean fold increase in serum antibody titer post-vaccination over Day 1 (baseline) at Days 7, 28, 35, 56, 112, 224 and 336 (Phase 1a); Days 7, 14, 28, 56, 84, 168 and 336 (Phase 1b)
 - Neutralizing activity against multiple variant spike protein-expressing pseudoviruses, and/or PRNT neutralizing activity against multiple variants of SARS-CoV-2 virus and the variant (B.1.351) in all participants
 - RBD antibody titers against wild-type variant spike protein measured by ELISA

Exploratory Immunogenicity Endpoints/Outcome Measures

- Geometric mean number of IFN- γ -positive cells per 10⁶ PBMCs by ELISPOT assay post-vaccination over Day 1 (baseline) at Days 7, 28, 35, 56 and 336 (Phase 1a); Days 7, 14, 28 and 336 (Phase 1b)

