7.10 Sixty Minutes Post-Immunization

The following safety observation procedures will be performed immediately following immunization with the study vaccine for all participants:

Participants will remain in the clinic for at least 60 minutes post vaccination. The observation period will include an assessment of immediate solicited local and systemic reactions. Any unusual signs or symptoms reported during the initial 60 minutes of observation will prompt continued close monitoring. Based on their condition, participants may be asked to remain in the clinic for more than 60 minutes after the immunization (reason will be recorded in source data). All data (including assessment of solicited local and systemic reactions) will be recorded in the source document during and after the post-observation period. Refer to [Section 8](#) for assessment of AEs and/or solicited local and systemic reactions.

During the injection visit, participants will be provided Diary Cards, a measurement device template (in mm) for measuring solicited local reactions (erythema [redness] and swelling), and an oral digital thermometer for recording daily temperature (in °C). The participants will be:

- Instructed how to examine swelling in the neck and axilla and record any unusual feeling and/or swelling in their Diary Cards.
- Requested to record their individual data in their Diary Cards, as described above.
- Advised that they will be asked about the occurrence of any symptoms or events requiring medical attention and the use of concomitant medication up to Day 336.
- Informed that they should bring their Diary Cards to the next visit after vaccination. The staff will review the Diary Cards entries with the participant.
- Advised on how to contact study personnel. Participants will be advised to immediately contact the investigator (or his/her designee), in the event of an SAE or change in health.
- Informed to notify their health care professional(s) (e.g., primary care physician) that they are participating in a clinical research study of a SARS-CoV-2 vaccine.

Measurement of vital signs (including blood pressure, heart rate, respiration, and oral temperature). Vital signs will be taken after 60 minutes (+ 10 minutes window) (with the participant in a seated position as per study center standard procedure. Any out-of-range

measurements will be assessed by the investigator (or his/her designee) and any further action will be determined upon his/her medical decision.

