If any of the solicited local or systemic reactions persist beyond Day 7, these will also be recorded as an AE. In this case, the AE start will be set as 7 days post vaccination. The participant will be requested to note when the AEs resolves and report this information to the investigator or clinic staff at the next visit at the study center or contact.

The clinical importance of AE will be determined based upon the investigator's judgment. The investigator must ensure that any sample obtained to follow-up an AE is properly labeled and stored. The investigator and others responsible for care of the participants should institute any supplementary investigations of significant AEs based on the clinical assessment of the likely causative factor. This may include seeking the opinion of a specialist in the field of the AE.

All AEs occurring within 28 days after vaccination must be recorded in the study source documents at the site or Diary Cards and reported in the "Adverse Event" screen in the participant's eCRF, irrespective of intensity or whether or not they are considered vaccination-related. Thereafter, from Day 28 through completion of the Day 336 visit, participants will need to record all AEs in their Diary Cards. Adverse events, pregnancy and SAEs will be monitored and recorded in the eCRF. Serious adverse events and pregnancy will be reported to Pharmacovigilance.

Treatment Emergent Adverse Event (TEAE)

TEAE is an event that emerges during treatment having been absent pre-treatment, or worsens relative to the pre-treatment state (ICH E9). The period of observation for collection of TEAEs extends from the time the participant receives the first dose of study drug through the last study visit.

Medically-Attended Adverse Events (MAAE)

- A condition prompting emergency room visit, physician visit not related to a common disease/not a routine visit or an SAE not related to a common disease SAE.

Serious Adverse Event (SAE)

During clinical investigations, adverse events may occur which, if suspected to be medicinal product related (adverse drug reactions), might be significant enough to lead to important changes in the way the medicinal product is developed (e.g., change in dose, population, needed monitoring, consent forms).

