For each symptom the participant experiences, the participant will be asked if the participant received medical attention defined as hospitalization, or an otherwise unscheduled visit to or from medical personnel for any reason, including emergency room visits. This information will be recorded in the eCRF.

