10 STATISTICAL METHODS

10.1 Outcome Measures

10.1.1 Primary Endpoints/Outcome Measures

Rate and severity of local and systemic solicited adverse events (AEs) during 7 days after each study vaccination

Rate and severity of unsolicited AEs at Study during 28 days after each study vaccinations

Rate and severity of medically attended adverse events (MAAEs) during 28 days after each study vaccinations

Rate of serious adverse events (SAEs) during 28 days after each study vaccinations AEs leading to discontinuation of study vaccination

AEs leading to study discontinuation

Rate and severity of laboratory abnormalities (hematology, biochemistry, urinalysis) at Day 56 and 28 days after each study vaccination

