6.3 Safety Analyses

6.3.1 Adverse Events (AEs)

6.3.1.1 General Guidance on AEs

All AE related Tables and Listings will be analyzed using the SC. All adverse-events in the SC will be presented in listings. Only Treatment-Emergent Adverse Events (TEAEs) will be summarized in tables. TEAEs include: 1) AEs with an onset on or after the first vaccination dose and 2) AEs that worsen relative to the pre-treatment state. The period of observation for collection of TEAEs extends from the time the participant receives the first dose of vaccine through the last study visit.

Adverse events will be coded to the System Organ Class (SOC) and preferred term (PT) level using the Medical Dictionary for Regulatory Affairs (MedDRA dictionary).

TEAEs missing severity will be summarized as “missing” in summary tables.

The summary tables for unsolicited AEs will use the following algorithms for counting the subject:

- System Organ Class row: Subjects experiencing the same AE System Organ Class several times will only be counted once.
- Preferred term row: Subjects experiencing the same AE preferred term several times with different grades will only be counted once with the maximum grade.
- Any event row: Each subject with at least one adverse event will be counted only once at the maximum grade no matter how many events they have.

Unless otherwise stated, AEs will be ordered alphabetically by SOC and in descending order of frequency by PT.

The summary tables for the rate and severity of solicited AEs will be presented by the terms defined on the eCRF.

Other types of events collected are defined as follows:

- 1) Medically-Attended Adverse Events (MAAE) – A condition prompting emergency room visit, physician visit not related to a common disease/not a routine visit or an SAE not related to a common disease SAE.
- 2) Serious Adverse Event (SAE) – Any untoward medical occurrence that *at any dose* results in death, is life-threatening, requires hospitalization or prolongation of existing hospitalization, results in disability/incapacity, is a congenital abnormality/birth defect in an offspring of a study participant, or is another medically important event.

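### The MAAE endpoint leaves out visits and SAEs for an undefined 'common disease', and no rule turns the recorded medical visits into MAAEs

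*Protocol*

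**What the plan says.** Protocol 4.10 lists as primary "Rate and severity of medically-attended adverse events (MAAEs) during 28 days after each study vaccination". Protocol 10.1.1 and SAP section 2 repeat it, and both documents make the whole-study MAAE rate a secondary endpoint.

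The definition is in Protocol 8.1. After emergency room visits, it admits a "physician visit not related to a common disease/not a routine visit or an SAE not related to a common disease SAE". SAP 6.3.1.1 carries the same definition, opening "A condition prompting emergency room visit, physician visit not related to a common disease/not a routine visit". The term *common disease* occurs only in these two places. The glossary, the abbreviation lists and the adverse event sections do not explain it.

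Data collection is described in Protocol 8.6 under medically attended visits. For each symptom, the participant is asked about "medical attention defined as hospitalization, or an otherwise unscheduled visit to or from medical personnel for any reason, including emergency room visits", and "This information will be recorded in the eCRF". Protocol 7.10 is equally broad: participants are "Advised that they will be asked about the occurrence of any symptoms or events requiring medical attention". SAP 6.3.1.2 then counts subjects with unsolicited MAAEs but gives no rule for getting from the recorded visits to an MAAE.

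**The concern.** An MAAE endpoint is useful because it needs no opinion about cause: either the event led to medical contact or it did not. The definition here adds an opinion, namely whether the illness is common, and gives no standard for it. Two sites, or two programmers, could derive different primary-endpoint counts from the same records.

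The doubt falls on events that are likely in this trial. Protocol 4.2 lists cough, sore throat and diarrhea among the symptoms under surveillance, and Protocol 4.3 encourages participants with suspected COVID-19 to seek care or testing from their usual provider where appropriate. Whether such a visit is an MAAE depends on whether someone calls the illness common.

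**Working it through.** The plan states no MAAE rate and no sample size based on MAAEs, so there is no figure to reproduce. The check compares the two texts and then uses simple arithmetic on the group sizes.

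**Step 1. The texts side by side**

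| Event | Recorded as medical attention (Protocol 8.6) | MAAE (Protocol 8.1, SAP 6.3.1.1) |
|---|---|---|
| Emergency room visit | Yes | Yes |
| Unscheduled physician visit outside the ER, illness not judged common | Yes | Yes |
| The same, illness judged common | Yes | No |
| Direct hospital admission, illness judged common | Yes | No, though it is an SAE |
| Unscheduled contact outside the ER with medical personnel who are not physicians | Yes | Not covered, unless an SAE that is not judged common |
| SAE with no hospitalisation or visit, not judged common | No | Yes |

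The third and fourth rows depend on the undefined term. The fifth and sixth differ for other reasons and also need a mapping rule. A further gap is that 8.6 asks symptom by symptom, while 8.1 defines an MAAE by condition.

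**Step 2. Effect of one reclassified participant**

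Group sizes are from Protocol Table 3: 20 in each of G1 to G3, and 27 in each of G4 and G5. If all are vaccinated and so enter the denominator:

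- Phase 1a: 1/20 = 5.0 percentage points
- Phase 1b: 1/27 = 3.7, or about 4, percentage points

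**Step 3. Timing against unblinding**

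Protocol 8.7.1 unblinds each phase after the DSMB has reviewed safety data through Day 56. On the nominal schedule the last primary window closes at:

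- Phase 1a: second injection on Day 28, and 28 + 28 = Day 56
- Phase 1b: single injection on Day 1, and 1 + 28 = Day 29

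The primary windows therefore close before unblinding. MAAEs are collected to Day 336, so events from after unblinding to the end of the study can be judged common or not with the arm known. They enter only the whole-study secondary endpoint.

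**The case against.** Collecting broadly and analysing a narrower set is ordinary practice. A reader might infer that the plan holds two rival definitions of MAAE. It does not: Protocol 8.1 and the SAP agree, and 8.6 defines medical attention without using the label MAAE. That answers a charge of contradiction. It does not supply the meaning of *common disease* or the missing mapping.

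A reader might also infer that the eCRF has no field for the judgement, so that the endpoint cannot be derived. The eCRF and its completion guide are not among the documents, so that cannot be known. What can be said is that the documents describe no such field and no rule.

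The consequences are limited, and this part of the objection stands:

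- An admission through the emergency room is an MAAE even for a common illness.
- All AEs within 28 days of vaccination are recorded, unsolicited AEs and SAEs are primary endpoints of their own, and both are listed.
- Fisher's exact test is planned only for solicited AEs, and no stopping rule refers to MAAEs.

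Finally, a sponsor could define *common disease* instead of deleting it. That would also remove the ambiguity. However, it keeps a filter on perceived commonness in an endpoint meant to catch unexpected imbalances, and it fits the 8.6 record less directly.

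**Conclusion.** The point holds in a limited form. As written, the MAAE endpoint turns on an undefined term, and no passage links the recorded contacts to it. Physician visits outside the emergency room and direct admissions for an illness judged common fall out of the MAAE rate, by a judgement that can vary between sites.

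The loss is to the MAAE rate and not to safety reporting as a whole, because the same events remain in the AE and SAE endpoints. Each reclassified participant shifts a group's rate by about 5 points (n = 20) or 4 points (n = 27). How many would be reclassified cannot be derived, since the documents give neither an expected rate of medical contact nor the share that would be called common.

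A reader might take the early unblinding to threaten the primary endpoint. The nominal windows do not support that: judgement with the arm known is a concern only for the whole-study secondary endpoint.

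**What to change.** Reconcile Protocol 8.1, Protocol 8.6 and SAP 6.3.1.1 on one definition derived from the 8.6 record:

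- An MAAE is any AE that leads to hospitalisation, an emergency room visit or another unscheduled visit to or from medical personnel, **or** any SAE. Keeping the SAE limb retains a serious event that involved no visit.
- Visits that the protocol itself requires or the investigator requests do not count. Examples are the unscheduled potential COVID-19 illness and convalescent visits (Protocol 4.3) and a return to the clinic that the investigator asks for (Protocol 8.2). Without this exclusion, study procedures would create MAAEs.
- Delete both common-disease clauses.
- State in the SAP how the symptom-level eCRF entries map to an MAAE.
- If the sponsor wants the narrower count, report it as a supplementary summary using a prespecified list of common diseases.

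The SAP revision is dated October 2022 and Phase 1a is planned to be unblinded after its Day 56 review, so record the change and its date in SAP section 7. A rule that needs no judgement can still be applied after unblinding.

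The cost is mainly wording, plus a check that the eCRF separates study-required and investigator-requested visits from other unscheduled ones. Otherwise it uses information that 8.6 already has recorded. The downside is a somewhat higher MAAE rate in all groups.

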8.2 Solicited Local and Systemic Reactions

The intensity of the solicited local and systemic reactions will be graded as: (1) mild, (2) moderate, (3) severe, or (4) potentially life threatening ([Table 4](#)). Their causal relationship with the study vaccine will be assessed by the investigator (definitely not related, probably not related, possibly related, probably related or definitely related). The solicited local and systemic reactions will be measured and reported by each study participant from the time of study vaccine administration up to seven days post vaccination.

Any AE/SAEs, any signs, symptoms or diseases experienced by the participant following the signature of the informed consent but before administration of the vaccine will be recorded in source data as pre- dose events (as a part of participants' medical history).

For any unsolicited AEs greater than Grade 2 (moderate), the participant should inform the investigator within 48 hours of the time of the event. The investigator may request that the participant return to the clinic for evaluation. The investigator will document the review and follow-up of such events on the source document.

Any clinical laboratory test result that meets the criteria for an AE in the absence of appropriate and/or adequate clinical diagnosis should be reported as an AE, unless the result is considered normal or not clinically significant for the current trial participant population, as determined by the Investigator.

Clinical laboratory parameters and other abnormal assessments qualifying as adverse events or serious adverse events

In absence of diagnosis, abnormal laboratory findings (e.g., clinical chemistry, hematology, urinalysis) or other abnormal assessments (e.g., physical examination findings) that the investigators judge to be clinically significant will be recorded as AE or SAE if they meet the definition of an AE or SAE. Clinically significant abnormal laboratory findings or other abnormal assessments that are present at baseline and significantly worsen following the start of the study will also be reported as AEs or SAEs. The investigator will exercise his or her medical and scientific judgment in deciding whether an abnormal laboratory finding or other abnormal assessment is clinically significant.

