8.6 Assessment of Adverse Events

Each AE is to be evaluated for duration, severity (intensity), outcome, and causal relationship to the investigational drug.

The investigator will assess the maximum intensity that occurred over the duration of the event for all AEs (including SAEs) recorded during the study. The assessment will be based on participant reporting, the investigator's clinical judgment and FDA Guidance for industry (Toxicity grading scale for healthy adult and adolescent volunteers enrolled in preventive vaccine clinical studies, September 2007) and presented in [Table 5](#), [Table 6](#) and [Table 7](#).

The intensity of each sign or symptom reported will be graded using the 4-point severity scale shown in [Table 4](#).

Table 4: Severity Scale

Grade 1 (Mild)	No interference with daily activity
Grade 2 (Moderate)	Some interference with daily activity but not requiring medical intervention
Grade 3 (Severe)	Prevents daily activity and requires medical intervention
Grade 4 (Potentially life threatening)	Requiring Emergency Room (ER) visit or hospitalization

Table 5: Toxicity Grading Scale for Solicited Local Adverse Events

Solicited Local AE	Grade 1	Grade 2	Grade 3	Grade 4
Pain (pain without touching)	Does not interfere with activity	Repeated use of non-narcotic pain reliever >24 hours or interferes with activity	Any use of narcotic pain reliever or prevents daily activity	Emergency room (ER) visit or hospitalization
Tenderness (pain when area is touched)	Mild discomfort to touch	Discomfort with movement	Significant discomfort at rest	ER visit or hospitalization
Pruritus associated with injection See also skin: pruritus (itching - no skin lesions)	Itching localized to injection site AND relieved spontaneously or with <48 hours treatment	Itching beyond the injection site but not generalized OR Itching localized to injection site requiring ≥48 hours treatment	Generalized itching causing inability to perform usual social & functional activities	NA
Erythema/Redness ^a	2.5–5 cm	5.1–10 cm	>10 cm	Necrosis or exfoliative dermatitis
Induration/Swelling ^b	2.5–5 cm and does not interfere with activity	5.1–10 cm or interferes with activity	>10 cm or prevents daily activity	Necrosis

Abbreviations: AE=adverse event; NA=not applicable

^a In addition to grading the measured local reaction at the greatest single diameter, the measurement was recorded as a continuous variable.

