^b Induration/Swelling was evaluated and graded using the functional scale as well as the actual measurement. Source: (US Food and Drug Administration 2007)

Table 6: Toxicity Grading Scale for Solicited Systemic Adverse Events

Systemic (General)	Mild (Grade 1)	Moderate (Grade 2)	Severe (Grade 3)	Potentially Life-Threatening (Grade 4)
Nausea/vomiting	No interference with activity or 1-2 episodes/24 hours	Some interference with activity or >2 episodes/24 hours	Prevents daily activity, requires outpatient IV hydration	ER visit or hospitalization for hypotensive shock
Diarrhea	2 - 3 loose stools or < 400 g/24 hours	4 - 5 stools or 400-800 g/24 hours	6 or more watery stools or >800 g/24 hours or requires outpatient IV hydration	ER visit or hospitalization
Headache	No interference with activity	Repeated use of non-narcotic pain reliever >24 hours or some interference with activity	Significant; any use of narcotic pain reliever or prevents daily activity	ER visit or hospitalization
Fatigue	No interference with activity	Some interference with activity	Significant; prevents daily activity	ER visit or hospitalization
Myalgia	No interference with activity	Some interference with activity	Significant; prevents daily activity	ER visit or hospitalization

Abbreviations: ER=emergency room; IV=intravenous Source: (US Food and Drug Administration 2007)

Table 7: Toxicity Grading Scale for Solicited Other Adverse Events

Vital Signs	Mild (Grade 1)	Moderate (Grade 2)	Severe (Grade 3)	Potentially Life-Threatening (Grade 4)
Fever ^a (°C) ** (°F) *	38.0–38.4 100.4–101.1	38.5–38.9 101.2–102.0	39.0–40 102.1–104	>40 >104
Tachycardia – beats/min	101–115	116–130	>130	ER visit or hospitalization for arrhythmia
Bradycardia – beats/min ^b	50–54	45–49	<45	ER visit or hospitalization for arrhythmia
Hypertension (systolic) - mm Hg	141–150	151–155	>155	ER visit or hospitalization for malignant hypertension
Hypertension (diastolic) - mm Hg	91–95	96–100	>100	ER visit or hospitalization for malignant hypertension
Hypotension (systolic) – mm Hg	85–89	80–84	<80	ER visit or hospitalization for hypotensive shock
Respiratory Rate – breaths/min	17–20	21–25	>25	Intubation

Abbreviations: ER=emergency room.

Note: Subject were at rest for all vital sign measurements

^aOral temperature; no recent hot or cold beverages or smoking

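### Protocol sections 8.2 and 8.6 direct solicited reactions to two severity scales that differ at Grade 3 for most items and at Grade 4 for some, with no order of precedence

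*Protocol*

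**What the plan says.** Four places in the protocol bear on how a solicited reaction is graded.

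- Section 8.2: "The intensity of the solicited local and systemic reactions will be graded as: (1) mild, (2) moderate, (3) severe, or (4) potentially life threatening", with Table 4 given as the reference.
- Section 8.6, first instruction: the intensity assessment rests on participant reporting, clinical judgment and the FDA guidance ("Toxicity grading scale for healthy adult and adolescent volunteers enrolled in preventive vaccine clinical studies, September 2007"), presented in Tables 5, 6 and 7. These tables carry titles such as "Toxicity Grading Scale for Solicited Local Adverse Events".
- Section 8.6, second instruction: "The intensity of each sign or symptom reported will be graded using the 4-point severity scale shown in" Table 4.
- Section 10.6.2: local and general events are evaluated with the FDA scale, with a reference back to 8.5 and 8.6.

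The SAP uses severity (6.3.1.1 and 6.3.1.2) and Grade 4 (5.5.1) without naming a grading table. Section 6.3.1.1 says solicited severity is shown by the terms on the eCRF.

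The grade is used in two places. The rate and severity of solicited events over 7 days is the first-listed primary endpoint (protocol 4.10 and 10.1.1; SAP section 2). Any Grade 4 event within 7 days of an injection is an individual stopping criterion (protocol 10.7; SAP 5.5.1), and these individual criteria feed the two-participant trial-level rule.

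**The concern.** If Table 4 were only a set of labels for the four grades, the double reference would be harmless. It is not: it has its own criteria, and they are not those of Tables 5 to 7. An investigator following 8.2 and one following the first instruction in 8.6 can each comply with the protocol and give the same reaction different grades.

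The reported severity distribution for a primary endpoint is at stake. So is the aggregate event in 10.6.2, which takes the maximal severity across local and general events and so carries forward a shift in any one term. For some items, whether an event counts towards the Grade 4 stopping criterion is also affected.

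**Working it through.** This is a check of consistency, so there is no stated figure to reproduce. Table 4 was set against 11 reaction items: the five local items in Table 5, the five systemic items in Table 6, and fever from Table 7. The other vital-sign rows of Table 7 were left out.

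**Grade 3.** Table 4 requires "Prevents daily activity and requires medical intervention", so both conditions must hold.

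| Item | Grade 3 in Tables 5 to 7 (paraphrased) | Same as Table 4? |
|---|---|---|
| Pain | "Any use of narcotic pain reliever or prevents daily activity" | No |
| Tenderness | marked discomfort at rest | No |
| Pruritus | generalized, with loss of usual function | No |
| Erythema | diameter above 10 cm | No |
| Induration/swelling | above 10 cm, or activity prevented | No |
| Nausea/vomiting | activity prevented, with outpatient IV hydration | Close; counted as a match |
| Diarrhea | stool count, stool weight or IV hydration | No |
| Headache | narcotic use, or activity prevented | No |
| Fatigue, myalgia (two items) | activity prevented | No |
| Fever | 39.0 to 40 °C | No |

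Result: 10 of 11 differ. For pain, induration/swelling, headache, fatigue and myalgia, preventing daily activity is enough on its own.

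**Gap in Table 4.** Take fatigue that prevents daily activity for a day, with no medical intervention. Table 6 makes it Grade 3. In Table 4 it goes beyond the partial interference of Grade 2 but fails the second condition of Grade 3, so no grade fits.

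**A case with two different grades.** Redness above 10 cm that does not interfere with activity is Grade 3 in Table 5 and Grade 1 in Table 4.

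**Lower end.** Table 5 starts grading redness and swelling at 2.5 cm. Table 4 has no size threshold for Grade 1, so for these two items even whether an event is counted may depend on the table.

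**Grade 4.** Table 4 reads "Requiring Emergency Room (ER) visit or hospitalization".

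- Same criterion in substance for 6 items: pain, tenderness, diarrhea, headache, fatigue, myalgia.
- Different for 5 items: pruritus (no Grade 4 in Table 5), erythema (necrosis or exfoliative dermatitis), induration/swelling (necrosis), nausea/vomiting ("ER visit or hospitalization for hypotensive shock") and fever (above 40 °C). 6 + 5 = 11.

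The difference runs both ways. An emergency visit for vomiting without shock is Grade 4 only in Table 4. Necrosis without an emergency visit is Grade 4 only in Table 5.

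**Sensitivity of a threshold of two (illustration only).** The documents give no Grade 4 rate. With an assumed per-participant probability p, P(at least 2) = 1 − (1 − p)^n − np(1 − p)^(n−1). For p = 0.5%, 1%, 2% and 5% this is about 2%, 6%, 19% and 60% for the 40 VBI-2902a recipients (20 + 20), and about 1%, 3%, 10% and 39% for the 27 VBI-2905a recipients. This shows only that a count of two is sensitive to what is called Grade 4. It does not estimate the effect of changing tables.

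**The case against.** The natural reading is that Table 4 is the generic scale and Tables 5 to 7 are the specific scales for the terms they list. The table titles support this, and section 10.6.2 names the FDA scale. That carries weight for the analysis, but 10.6.2 does not withdraw the Table 4 instruction in 8.2 or the second one in 8.6, and stopping events are flagged as they occur, from grades assigned under section 8.

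A reader might infer that sites will in fact grade differently. The documents do not show that. The eCRF and diary card are not available and may fix the scale in practice.

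A reader might also infer that the choice of table generally decides whether the trial stops. Several limits stand against this:

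- Grade 4 agrees for 6 of 11 items.
- Fever above 40.0 °C is its own stopping criterion, which leaves only emergency visits for fever at or below that level.
- A possibly related SAE is also its own criterion. Section 8.1 counts emergency-ward admission as hospitalization and treats doubtful cases as serious, so many emergency visits would count under either table.
- The two-participant stop is lifted if review by the DSMB, sponsor and investigators, in consultation with the regulator, finds that participant safety is not affected.
- Group G4 receives one dose, so the individual-level rule has no later injection to withhold there.

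Finally, Fisher's tests compare rates of solicited events, not grades. For pain, headache, fatigue and myalgia the table does not change whether an event occurred. Observer-blinding also means the ambiguity is not tied to treatment arm. What remains is the description of severity within each arm, which is part of the primary endpoint.

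**Conclusion.** The contradiction is real and can be read directly from the protocol: two scales are assigned to the same events, no precedence is stated, the SAP does not settle it, and the criteria differ at Grade 3 for 10 of 11 items. The severity part of the first primary endpoint can change with the table applied. The effect on the Grade 4 stopping criterion is item-specific, mainly pruritus, erythema, induration/swelling and nausea/vomiting, and remains subject to the review clause.

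The size of the change cannot be derived. It is tempting to say that a Grade 3 rate of several percent would fall to zero under Table 4. That would need an event rate, the share of events without medical intervention, and the absence of any other Grade 3 event; the documents supply none of these. The item counts rest on treating the nausea/vomiting Grade 3 wording as equivalent to Table 4 and on leaving out the other vital-sign rows of Table 7. No view is taken on which scale or which Grade 4 definition is right.

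**What to change.** - Reconcile protocol 8.2, 8.6 and 10.6.2 so that each event class (solicited local, solicited systemic, fever and vital signs, unsolicited) has one named grading scale or an explicit order of precedence.
- Repeat that statement in SAP 6.3.1.
- Close the gap between Grades 2 and 3 in Table 4, so that an event preventing daily activity without medical intervention has a grade.
- Have the sponsor and DSMB reconcile the differing Grade 4 criteria and state which definition feeds the stopping rules in protocol 10.7 and SAP 5.5. Because this bears on stopping vaccination, the choice is theirs.

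The cost is wording in the protocol and SAP, plus matching eCRF and diary guidance. Events already recorded may need regrading, which is possible where the item-specific descriptors were captured, and reported Grade 3 rates may change as a result.
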